- PICU admission
- CVC placed within 72 hours of enrollment (tunneled such as PICC, Broviac or Hickman, or untunneled) and in place during hospitalization

Exclusion criteria:

- Pregnancy
- Non-English-speaking subjects and/or parent/guardian
- Platelet count < 20,000
- Active CVC infection-defined as positive blood culture from the in -situ CVC at time of enrollment
- Current radiographically confirmed VTE
- Currently receiving treatment doses of anticoagulation (heparin infusion >15U/kg/hr, enoxaparin injections \geq 2mg/kg/day or \geq 60mg/day)
- CVC diameter <1.9 Fr
- Current or previous diagnosis of Heparin Induced Thrombocytopenia or allergy to heparin or t-PA
- Med-a-port catheters
- Active internal bleeding
- Recent intracranial or intraspinal surgery
- Serious head trauma
- Intracranial conditions that may increase the risk of bleeding
- Bleeding diathesis
- Current severe uncontrolled hypertension

Any patient admitted to the ICU and meeting the above inclusion criteria will be approached for consent within 72 hours CVC placement. Randomization and administration of t-PA/heparin control treatment will be initiated within 24 hours of enrollment.

After 1:1 randomization, t-PA/heparin will be infused in the CVC for a dwell duration of 30 minutes-4 hours and then withdrawn (lock therapy) every 3 days until discharge from the PICU, CVC removal or a maximum of 10 doses received. Additional lumens will be treated on subsequent days. Any lumen requiring continuous infusion of vaso-active medication will not receive dwell therapy, evaluated on a day-to-day basis. Timing of instillation of study dwell medication will be adjusted so as not to interfere with medications for patient care. Other stopping points of t-PA treatment are in Section L.

E. TOTAL NUMBER OF HUMAN RESEARCH PARTICIPANTS PROPOSED FOR THIS STUDY AT THIS SITE AND GLOBALLY. WHAT ARE THESE NUMBERS BASED ON?

This single center, pilot study will enroll 20 subjects at CHW. This sample size was chosen for the ability to be internally funded and to complete pilot data collection in a timely manner, with anticipated grant submission for a multi-center study in 2020.

F. DRUGS OR PROCEDURES

Procedures to be completed for this study are as follows:

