After informed consent/assent, the patient will be randomized and assigned to either the treatment arm (t-PA lock) or control arm (heparin lock). Randomization will be stratified by age (<5 or ≥5 years old). Pharmacy will blind the study medication t-PA so that it is indistinguishable from the control arm. Randomization will be done in the investigational pharmacy prior to the dispensing of the t-PA/heparin. During enrollment, the unblinded assignment log will be kept in the locked investigational room in central pharmacy.

Study Treatment and Dosing

In subjects randomized to the t-PA (Alteplase; Activase®, Genentech, 1mg/cc concentration), dosing will comply with the CHW Policy and Procedure Protocol *t-PA Administration for Central Venous Access Devices (CVAD)*; subjects randomized to the control arm, standard of care heparin group, will receive an equivalent volume for weight of heparin 10 units/ml. The bedside RN will administer the study medication/heparin as per the above protocol. The CVC should be flushed with normal saline prior to infusion of t-PA/heparin. After dwelling time of 30 minutes-4 hours, t-PA/heparin control should be withdrawn, check for blood return in CVC and flush line with normal saline as per policy. Each lumen of multi-lumen CVC should be treated every 3 days until patient discharge from ICU, removal of CVC, or a maximum of 10 doses of t-PA/heparin control are received.

Patient weight	Volume T-PA/Heparin
0-10kg	0.5ml
10-20kg	1 ml
>20kg	2 ml

These doses by body weight have been approved by the FDA for and CHHS Patient Care Protocol (tPA Administration for Central Venous Access Devices (CVADs) for use in children with CVC and are not associated with significant bleeding. If a 2mg (ml) dose of t-PA is administered by bolus injection directly into the systemic circulation, rather than as a dwell within the CVC, the drug concentration would return to endogenous levels with 30 minutes.

Ultrasound imaging

At the end of the study period, a noninvasive ultrasound with doppler will be performed for research purposes to assess for asymptomatic thrombosis in the blood vessel of the CVC location.

G. RISK CATEGORY:

Both arms of the study: Risk Level (2) 45 CFR 46.405 - Research involving greater than minimal risk but presenting the prospect of direct benefit to the individual child subjects involved in the research.

H. RISKS AND THE PRECAUTIONS WHICH WILL BE TAKEN TO MINIMIZE RISK EXPOSURE

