Adverse events will be considered any change from baseline. Expected adverse events are listed in section H; this section also includes those events considered serious but expected within this protocol. Expected SAEs will be reported in aggregate at the study’s annual review. Any SUSAR experienced during the study will be reported per IRB’s Reportable Events guidelines. At completion of the study adverse event rates between the study group and heparin control group will be compared and included in any final study reports.

Serious Adverse Events

If any subject enrolled in the study experiences any serious adverse event, the study team and care team will discuss the likely cause of the events. If it is determined that the event is probably or definitely related to the t-PA/heparin control the study treatment can be discontinued at the discretion of the care team and study team. Subjects whose treatment is discontinued will be followed for 30 days after the last t-PA/heparin control dose or until hospital discharge, whichever occurs first.

K. ANTICIPATED BENEFITS ASSOCIATED WITH THE PROTOCOL TO HUMAN RESEARCH PARTICIPANTS AND SOCIETY

Benefit to the individual patient may include a decreased risk of CVC infection or VTE.

Benefit to society at large will be knowledge gained to optimally design multicenter interventional study to develop therapy to reduce the risk of central line infection and/or thrombosis. There is evidence that these complications result in unfavorable outcomes such as increased length of mechanical ventilation, increased length of stay, increased healthcare cost, and increased mortality.

L. STOPPING POINTS THAT WOULD NOT ALLOW THE STUDY TO CONTINUE AS PROPOSED

Withdrawal from study

The PI or subject's primary care team can withdraw the subject from this study due to

- Consent is withdrawn by subject's family
- Treating physician wishes to withdrawal subject for any reason

M. IS THERE A DATA SAFETY MONITORING BOARD IN PLACE? WHO ARE IT'S MEMBERS? HOW OFTEN DO THEY MEET?

There is no DSMB planned for this study.

N. DESCRIBE HOW THE CONSENT AND ASSENT PROCESS WILL TAKE PLACE. INCLUDE A LIST OF APPROPRIATELY TRAINED PERSONNEL WHO WILL BE INVOLVED.

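### Bleeding-risk exclusions are written for entry only, with no check before later dwells, and Section J sets two different adverse-event windows for a child stopped after a related SAE

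*Combined protocol and SAP*

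**What the plan says.** **Entry criteria.** The exclusion list in Section D includes a platelet count below 20,000, "Active internal bleeding", "Currently receiving treatment doses of anticoagulation", "Current severe uncontrolled hypertension" and intracranial conditions that raise bleeding risk. Section H repeats the platelet and anticoagulation items as a precaution, again as reasons to exclude a patient.

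**Dosing.** Section D gives study drug "every 3 days until discharge from the PICU, CVC removal or a maximum of 10 doses received". A lumen carrying a continuous vaso-active infusion "will not receive dwell therapy, evaluated on a day-to-day basis". Section F says that in the t-PA arm "dosing will comply with the CHW Policy and Procedure Protocol" for t-PA in central venous devices, and that the bedside nurse gives either study solution under that policy. Section H also names the policy as a precaution.

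**Stopping.** Section D adds: "Other stopping points of t-PA treatment are in Section L". Section L holds only withdrawal from the study: the investigator or the child's "primary care team can withdraw the subject from this study due to" withdrawn consent or the treating physician's wish, for any reason.

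**Adverse-event follow-up.** Sections H and J give a general window: the earlier of last dose plus 30 days and catheter removal plus 7 days, with chart review to 7 days after discharge if the catheter is still in. Section J applies this to every child with at least one dose. Under its serious adverse event heading, Section J lets treatment be stopped after a probably or definitely related event, then follows the child to the earlier of last dose plus 30 days and hospital discharge. Section J also plans a comparison of adverse event rates between arms.

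**The concern.** The exclusions mark children whom the protocol considers unsafe to dose, but their state can change during a PICU stay. One route is built into the trial: VTE is part of the primary outcome, and a child who develops one may start treatment-dose anticoagulation. That child would no longer be eligible, yet the written dosing rule ends only at PICU discharge, catheter removal or ten doses. The drug is blinded and Section M plans no DSMB, so the bedside team has little beyond its own judgement and the hospital policy to stop the next dwell.

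The second matter is observation time. A child discontinued after a related SAE has also had at least one dose, so both Section J windows apply to the same child and they end on different days. If related SAEs differ by arm, so may the time over which further events are captured, and the arms are to be compared on those events.

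**Working it through.** The plan gives no figure to reproduce on this point. The check sets the sections side by side and then does date arithmetic.

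**1. Where each condition is checked**

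| Condition | At entry | Before later dwells |
|---|---|---|
| Platelets < 20,000 | D, H | nothing written |
| Treatment-dose anticoagulation | D, H | nothing written |
| Active internal bleeding | D | nothing written |
| Severe uncontrolled hypertension | D | nothing written |
| Intracranial conditions | D | nothing written |
| Lumen on vaso-active infusion | not an exclusion | daily hold, D |

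The last row shows that the authors do write rules at dose level where they want them.

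**2. Doses that fall in the gap.** Inputs: one dose every 3 days, at most 10 (Section D). Assumed: one lumen, first dose on day 1. Dose k falls on day 1 + 3(k − 1), so on days 1, 4, 7, 10, 13, 16, 19, 22, 25 and 28. Suppose an excluded condition arises on day 5 (assumed) and the child stays in the PICU with the catheter in place:

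- to day 7: 1 dose still due (day 7);
- to day 14: 3 doses (days 7, 10, 13);
- to day 28: 8 doses (days 7 to 28).

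These counts illustrate the schedule. They do not measure risk, because the documents give no incidence for any of these conditions after entry.

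**3. The two windows.** Count days from the last dose, with discharge on day d and catheter removal on day r.

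- General window: min(30, r + 7) if the catheter is out before discharge. If it is still in, the reading used here is min(30, d + 7).
- SAE-discontinued window: min(30, d).

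| Case (assumed dates) | General | SAE-discontinued | Difference |
|---|---|---|---|
| Catheter in, d = 2 | 9 | 2 | −7 |
| Catheter in, d = 10 | 17 | 10 | −7 |
| Catheter in, d = 26 | 30 | 26 | −4 |
| Catheter in, d = 30 | 30 | 30 | 0 |
| r = 1, d = 3 | 8 | 3 | −5 |
| r = 5, d = 12 | 12 | 12 | 0 |
| r = 1, d = 20 | 8 | 20 | +12 |

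With the catheter in place the gap is 7 days for any discharge up to day 23, since 23 + 7 = 30, and then shrinks to 0 at day 30.

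**4. Sensitivity to the reading.** Section J does not say whether chart review ends the window or only adds to it. If it only adds, the general window in the second row could run to day 30 and the gap could reach 30 − 10 = 20 days. If instead the 7-day chart review also covers discontinued children, the gap closes in the catheter-in rows, but the rows with early removal still differ in both directions.

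**The case against.** **The hospital policy may already do this.** Section F ties dosing to it in both arms and Section H lists it as a bleeding precaution. A reader might infer that children will be dosed with no bleeding check at all. The documents do not support that: the policy is cited but not reproduced, and it may contain holds. What stands is narrower. The protocol writes no such hold and adopts none from the policy as a study rule. Section C says that t-PA at this hospital is reserved for occluded catheters, so holds suited to scheduled dwells cannot be assumed.

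**Discretion exists.** The treating physician may withdraw a child for any reason, and Section J allows treatment to stop after a related SAE. That is true, but neither route names a bleeding-risk criterion.

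**Exposure is small.** Dwells are withdrawn, and Sections F and H state that even a 2 mg systemic bolus would return to endogenous levels within 30 minutes. This tempers the likely harm. It does not explain why the same conditions bar a first dose but not a fifth.

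**Section L might be read as losing stopped children to follow-up.** It does not say so. Section J follows every dosed child and continues follow-up after a related SAE. The Section L wording is therefore a minor ambiguity and not a finding in its own right.

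**The window might be read as a bias of known direction.** It is not one: the difference runs both ways. A child on the SAE window has already had an event, so in a per-child comparison of any adverse event that child's status cannot change. Only later events of other types could be missed or added. This largely stands and limits the analysis concern.

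**Conclusion.** The concern holds in two parts, and the plan should be changed on both.

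First, the protocol text applies its bleeding-risk exclusions at entry and writes no check or hold for later dwells, of which there can be up to nine in one lumen. How often this would matter cannot be estimated from the documents, and the unseen hospital policy may already cover it. The reason to change is patient safety.

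Second, Section J sets two adverse-event windows for the same child. In the cases worked above they differ by between 7 days shorter and 12 days longer, on assumed dates and on the reading that chart review closes the window at discharge plus 7. The likely effect on the between-arm comparison in 20 children is small, but a drug-related event should not decide how long a child is observed for that comparison.

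Confidence is medium, mainly because the policy text is not available.

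**What to change.** **(a) Pre-dose hold.** Before each dwell in either arm, check the Section D bleeding-risk exclusions from data already in the chart: latest platelet count, active bleeding, treatment-dose anticoagulation, blood pressure, and any new intracranial condition. If any is present, including treatment-dose anticoagulation started for a new VTE, hold the study dose and give that lumen usual care. Record the hold separately from non-adherence, since adherence is an Aim 1 outcome. If the hospital policy already has such holds, adopt them in the protocol as study rules.

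**(b) One window for the comparison.** Use the general window of Sections H and J for all dosed children when adverse event rates are compared, including those discontinued, and state whether chart review closes that window or adds to it. Do not simply delete the SAE window: where the catheter is removed early in a long stay it is the longer of the two. Keep any longer follow-up after a related SAE for safety only.

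In the same amendment, a sentence in Section L could say that stopping study drug is separate from leaving the study.

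**Cost.** A protocol amendment, a short checklist, slightly fewer doses in both arms, and chart review to 7 days after discharge for the few discontinued children. No extra patients or tests are needed.
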